7 days via expired carbon monoxide testing and/or salivary cotinine, 2) obtain a follow-up salivary cotinine level on 100% of children to validate total smoking bans, and 3) complete assessment of outcomes. At 6 months, we will assess all caregivers via phone or email. We may contact them via social media or text messaging as well. Participant's privacy will be maintained when contacting them through social media by sending messages that only the participant can see via social media. PHI will not be used on these messages. Should the caregiver report abstinence and smoking bans, a home visit will be conducted to validate self-reported abstinence and total home smoking bans via salivary cotinine on the child and via expired carbon monoxide testing and/or salivary cotinine on the caregivers during home visits. Follow-ups may be conducted at CCHMC hospital if the participant already has a scheduled appointment at the hospital. If study staff is unable to make contact with the family during the course of the study to schedule the follow-ups an unannounced home visit may be conducted in order to complete study procedures.

Randomization. We will stratify by gender of the primary caregiver and stage of readiness to quit smoking where participants will be in stages 1: pre-contemplation, 2: contemplation 1 or 2, or 3: preparation;^{41,42} thus there will be 8 strata for randomization. A random block randomization scheme will be compiled by the study biostatistician prior to the start of the study, and used by the CRC to allocate participants to each condition. The biostatistician has a SAS® program for creating the randomization scheme that has been tested and used for other studies. As it is anticipated that there will be fewer male caregivers, the random blocks used will be smaller than for the females. The randomization scheme will be accessed by the CRC by logging into a dedicated website and entering the gender and readiness to quit stage, the study group assignment and a study identification number will be returned. Backup will be opaque envelopes, kept within the PED with stratification and study identification number marked on the outside.

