
Given our prior experience⁵⁴ and proposed techniques, we conservatively project an 80% retention rate at 6 months.

Outcome Measures. Primary outcomes will be caregiver prolonged abstinence and 7-day point prevalence of tobacco use at 6-weeks and 6-months. Secondary caregiver outcomes will include cigarettes smoked, quit attempts, readiness to quit, and use of NRT and cessation resources (QL, smokefreeTXT, smokefree.gov). Child outcomes will be presence or absence of total home/car smoking bans, reported SHSe, and number of SHSe-related PED visits and hospitalizations at CCHMC.

Baseline Assessment. (Table 1) The brief baseline assessment (T0) will be conducted using a self-administered electronic survey to be completed on a tablet computer. The assessment items chosen are empirically validated measures from studies conducted with low-income disadvantaged study populations.^{42,66-71,39,63-68} The items are brief, easily comprehensible, and take into account low literacy levels. They are as follows:

Table 1: Measures for Baseline and Follow-up Assessments by Assessment Point	T0	T1	T2
Demographics; Financial Strain, , Household Smokers,	✓		
Tobacco Use History, Nicotine dependence, , Motivation to Quit	✓	✓	✓
Risk Perceptions: Child; Benefits of Quitting: Child	✓	✓	✓
Child's SHSe, , Child SHSe - related PED visits or Hospitalizations	✓	✓	✓
Healthy Habits Lifestyle- daily: fruits/vegetables, screen time, exercise, sugary drinks	✓	✓	✓
SBIRT and HHC Satisfaction,	✓		
Prolonged abstinence, point prevalence, nicotine dependence, readiness to change, quit attempts		✓	✓
Cessation Resource utilization: NRT, QL, SmokefreeTXT, Smokefree.gov, or other resources	✓	✓	

1. Demographics and tobacco use. We will collect gender, age, race/ethnicity, level of education, employment status, , number of cigarettes smoked daily, time to the first cigarette of the day, nicotine dependence, number of attempts to quit >24 hours, use of pharmacological and/or behavioral treatments for quitting, motivation to quit using the Contemplation Ladder, and stage of change in readiness to quit.^{41,72} Questions will also be asked about marijuana use by the participant and household members; participants will not be required to answer these questions. Participants who consented prior to Version 11 of the protocol may be re-consented at follow-up such that we may obtain information about marijuana use.

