We will use GLMM to evaluate the relative effectiveness of the SBIRT versus HHC group on our primary outcomes: point prevalence and prolonged abstinence at 6-months. The analysis will be repeated with caregiver level differences between groups included as covariates. We will use mixed model analysis of covariance, with repeated measures to assess change (controlling for baseline differences between groups) to assess the effect of the SBIRT on secondary outcomes including reduction in use, number of quit attempts, and changes in readiness to quit. Kappa statistic will be used to assess agreement between the caregiver's self-report and the assessment of tobacco use based on expired carbon monoxide levels and/or salivary cotinine at 6 months. It is possible that use of and adherence to the NRT will influence outcomes in the intervention group. In addition, some of the participants in the control condition may obtain NRT during the study interval. We will examine NRT use or dose, defined as self-reported adherence, as a covariate in order to control for this possible relationship.

Analyses for Primary Aims 1-3.

Primary Aim 1, Hypothesis 1: We hypothesize that SBIRT participants will have higher prolonged abstinence and point prevalence cessation rates compared to those in the HHC group. As stated above, our primary approach to the analysis is using multiple imputation, with clinical counselors/intake coordinators/research coordinators included in the model. We shall then use analysis of covariance, to control for any baseline differences of caregivers between conditions. In addition we will also control for motivation to quit, considered a priori as a potential covariate, using the score on the contemplation ladder. As we are stratifying on motivation to quit and caregiver gender, we will initially enter this into the model as an interaction. To address child cotinine as the 6-month outcome, we will use a t-test and then an analysis of covariance to incorporate the variables different at baseline. Incorporating the 6-week outcome values, we will use GLMM invoking GEE for the repeated

measures and also a model including covariates. This approach will be used to assess the intervention's effect on abstinence and point prevalence and child cotinine.

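### The plan does not say whether the readiness stage used at randomisation or the Contemplation Ladder score enters the Aim 1 model, and its primary step names neither stratifier

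*Combined protocol and SAP*

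**What the plan says.** All references are to the combined protocol and SAP.

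- **Study Design Overview, Randomization.** The stratifiers are stated: "We will stratify by gender of the primary caregiver and stage of readiness to quit smoking". The levels follow: "participants will be in stages 1: pre-contemplation, 2: contemplation 1 or 2, or 3: preparation". The paragraph then concludes: "thus there will be 8 strata for randomization". The coordinator obtains an allocation by "entering the gender and readiness to quit stage" on a website. No Ladder score is involved.
- **Baseline Assessment, item 1.** Two measures are collected: "motivation to quit using the Contemplation Ladder, and stage of change in readiness to quit". Here motivation is the Ladder and readiness is the stage.
- **Analyses for Primary Aims 1-3, Primary Aim 1.** The primary approach is multiple imputation with the interventionist in the model. Covariate adjustment comes after that: "we will also control for motivation to quit, considered a priori as a potential covariate, using the score on the contemplation ladder". The next sentence reads: "As we are stratifying on motivation to quit and caregiver gender, we will initially enter this into the model as an interaction". Stage of readiness is not named anywhere as a term in an Aim 1 model.

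**The concern.** The factor that defines the allocation lists is called stage of readiness in the design section and motivation to quit in the analysis section. In the analysis section the only instrument attached to that name is a different one. An analyst who follows the Aim 1 paragraph literally would fit Ladder by gender. An analyst who looks back to the Randomization paragraph would fit stage by gender. Each could cite the plan.

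Three further points are left open. The model labelled primary carries neither stratifier by name. The interaction is not defined: it could be between the two stratifiers, or between them and treatment. The word initially implies that the term may later be dropped, but no rule is given.

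What is at stake is pre-specification and a little precision. Balancing the arms within strata removes some between-arm variation. If the model ignores the strata, its standard error does not reflect that gain and the test is slightly conservative. Outcomes are also sparse, so the choice of terms should be settled before results are seen.

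**Working it through.** **1. The plan's own figure, 8 strata.** Strata = genders x stages.
- Contemplation 1 and contemplation 2 as separate levels: 2 x 4 = 8, which matches.
- The three numbered stages as printed: 2 x 3 = 6, which does not.

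The stated count therefore requires four stage levels, although the numbering shows three.

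**2. Degrees of freedom with four stages.** Main effects use (4 - 1) + (2 - 1) = 4. A stage-by-gender interaction adds 3 x 1 = 3, for a total of 7.

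**3. Events available.** From Sample Size and Power Estimates: 300 completers per arm and prolonged abstinence of 2.1% and 7%. Expected events are 300 x 0.021 + 300 x 0.07 = 6.3 + 21 = 27.3. Spread over 8 strata this averages 27.3 / 8 = 3.4 each. It will be fewer in the male strata, since the plan expects fewer male caregivers. This supports main effects over a full interaction.

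**4. What the choice of term does to the test.** This was checked by simulating stratified block randomisation and fitting three logistic models to the same simulated trials.

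Inputs from the documents: 300 per arm; control point prevalence 6.3%; detectable increase 6.4 points, giving 12.7%.

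Assumed, because the documents do not give them:
- two-sided 5% test;
- three stages split 40/40/20, and 20% men;
- quit odds ratio of 1.5 or 2.5 per stage step, with no gender effect;
- correlation of 0.5 or 0.8 between the Ladder score and the latent variable behind stage;
- blocks of 4 (women) and 2 (men);
- complete data, with no imputation and no interventionist term.

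There were 3,000 runs per setting. Each cell gives no stratifier / Ladder x gender / stage + gender.

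| Odds ratio per stage | Correlation | Type I error, % | Power, % |
|---|---|---|---|
| 1.5 | 0.5 | 4.53 / 4.87 / 4.67 | 76.60 / 76.77 / 77.00 |
| 1.5 | 0.8 | 4.63 / 4.97 / 4.90 | 75.17 / 75.40 / 75.77 |
| 2.5 | 0.5 | 4.60 / 4.77 / 4.90 | 77.23 / 77.97 / 78.93 |
| 2.5 | 0.8 | 4.33 / 4.83 / 4.83 | 75.73 / 77.17 / 77.40 |

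- Power lost by Ladder instead of stage: 0.23, 0.37, 0.96 and 0.23 points.
- Power lost by no stratifier instead of stage: 0.40, 0.60, 1.70 and 1.67 points.
- Monte Carlo error: sqrt(0.05 x 0.95 / 3000) = 0.40 points for type I error; sqrt(0.77 x 0.23 / 3000) = 0.77 points for power. Contrasts between models are less noisy than this because the models share the same simulated trials.
- Mean type I error with no stratifier: (4.53 + 4.63 + 4.60 + 4.33) / 4 = 4.52%. Over 12,000 runs the Monte Carlo error is sqrt(0.05 x 0.95 / 12000) = 0.20 points, so the conservatism is real but slight.

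Only the contrasts between models matter here. The overall power level is a separate question.

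**The case against.** A reader might infer that the primary analysis omits a factor the trial randomises by. The documents do not support that. The sentence on stratification opens by stating that the trial stratifies, so it expresses an intention to enter the stratifiers. The Ladder sentence before it describes a covariate and need not define the stratifier. Gender is included on either reading. The plan also uses the two words interchangeably elsewhere: the Aim 3 mediator is motivation in Hypothesis 3 under Purpose, and readiness in the Aim 3 analysis. The natural reading may well be that stage is meant. This stands, and it limits the point to ambiguity.

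A reader might also infer from the 6-versus-8 count that the website and the allocation lists could use different stages. Nothing in the text suggests this. The Randomization paragraph describes one scheme, compiled by the biostatistician and reached through the website, and the stated 8 resolves to four stages by two genders. What remains is that the printed numbering should show four levels.

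It is also fair to say that the statistical harm is close to nil if the Ladder is used, since type I error stays nominal in the simulation. That stands too. It does not settle which model is primary, and the step carrying that label names neither stratifier.

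**Conclusion.** The point holds as a lack of clarity with small impact. The plan gives the stratifier two names, ties the second to a different instrument, and does not name either stratifier in the primary step. Under the assumed inputs, using the Ladder in place of stage costs about 1 point of power or less with no inflation of type I error. Leaving both stratifiers out gives a type I error of 4.3-4.6% and costs up to about 1.7 points of power against stage plus gender.

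These sizes rest on the assumed stage split, strength of prediction, Ladder-stage correlation and significance level. They also rest on a three-level stage, whereas 8 strata imply four. The conclusion that the plan should name its terms rests on the text alone. It is worth correcting because it costs almost nothing and closes a choice that could otherwise be made after the data are seen.

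**What to change.** 1. **Primary Aim 1.** Replace the sentence on the interaction with a statement that the primary model for both prolonged abstinence and point prevalence includes main effects of readiness stage, as used at randomisation, and of caregiver gender. Make clear that this applies to the multiple-imputation analysis labelled primary, not only to the later adjusted models. The Ladder score may stay as an additional a priori covariate. If an interaction is still wanted, define it and present it as secondary.
2. **Randomization.** List the stage levels so that they agree with 8 strata, showing contemplation 1 and contemplation 2 separately. Stage plus gender then uses 4 degrees of freedom, not 3.

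The cost is about two sentences and no new data collection. Stage is a baseline item and is entered to obtain the allocation. The plan does not say that the website retains the entered stage, so the trial team should confirm that it does.

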Sample Size. Our estimate of the number of caregivers that we plan to enroll is based on the average number of unique patients and the smoking prevalence of caregivers seen in a 12-month period in the PED at CCHMC. Based on enrollment in previous studies (which had average annual enrollment of 300-350 caregivers), and a 30 month chart review on the number of annual visits for patients with SHS-related complaints (at least 6,000), we are conservatively expecting to enroll 300 caregivers who smoke over 12 months, for a total of 750 caregivers in 30 months. To obtain the effective sample size for power analyses of outcomes, the sample size must be adjusted for potential attrition of approximately 20% at 6 months, although all efforts will be used to decrease this attrition rate, leaving a total of 600; 300 per group.

Estimate of effect sizes: Evaluation of outcomes. Based on the recommendations of Hughes et al.,^{85,86} we will use 2 criteria for abstinence: 6-month point prevalence and prolonged abstinence at 6-months. Based on a similar prior study, we expect that 6-month point prevalence in the HHC condition will be 6.3%.⁵⁴ For prolonged abstinence, we are basing our estimation on the 2.1% rate for the HHC and 7% rate for SBIRT. We are conservatively estimating a point prevalence cessation rate of 6.3% and prolonged abstinence rate of 2.1% in the HHC group.⁵⁴ We are basing our estimate of 6-month point prevalence of the SBIRT group on the odds ratio derived from meta-analyses assessing the effectiveness of NRT vs. a control, ranging from 1.4-4.6,⁵⁴ to give a cessation rate of 10-12% in the SBIRT group. However, since a clinical counselor/intake coordinator/research coordinator will be conducting the intervention, we expect high compliance in implementation. Thus, we are estimating a cessation rate of 12% in the SBIRT group. Similarly, for prolonged abstinence, we are assuming a rate of 7% in the SBIRT group.

Power (Table 2). Power analyses are based on estimates of differences in both 6-month point prevalence and 6-month prolonged abstinence between groups. With 300 subjects in each group, we would have 80% power to detect an increase of 6.4% in cessation rate. However, assuming a multiple imputation approach, we would be able to detect a 5.5% increase in cessation rate.

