For 6-month abstinence, we can detect an increase of 4.5% with 300 subjects per group and 4.2% with the multiple imputation assumption. These estimates are consistent with the predicted cessation rates shown above and published rates.^{54,93} For analyses based on regression techniques, using hierarchical linear modeling, sample sizes will be more than sufficient. The effect sizes of interest for these analyses are the correlation

Table 2: Estimated Power for varying sample size

N / group	Odds ratio 80% power- prevalence	Odds ratio 80% power- abstinence	Assumption
300	2.16	3.29	20% loss
375	2.00	3.05	Multiple Imputation

coefficients and squared, semi-partial correlations (squared=incremental R^2). To predict caregiver level variables (Primary Aim 1), with a sample size of 750 and 20% lost to follow-up, we will have >80% power to detect a correlation of 0.11 ($r^2=0.013$). For examination of smoking bans (Primary Aim 2), these samples sizes would allow us to detect a difference of 12% with 80% power with 300 per group assuming a rate of between 50% and 65% in the HHC group. Using multiple imputation and 375 per group, we could detect a difference of 11% with 80% power.

Analytic Plan

Data analyses will be conducted at CCHMC and at the University of Cincinnati. A DTA will be established with study investigators at the University of Cincinnati. Data will include demographics, smoking behavior, data from the parent assessments, clinical data, and EMR data. The data will be a limited data set stripped of identifiers. It will be shared on an encrypted file.

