Preliminary Analyses. Univariate and bivariate examination of variables will be done first. Distributional properties of the continuous outcome variables will be examined. To control for non-normal distributions and heterogeneous error variances, we will use logarithmic transformation and report geometric means and associated 95% confidence intervals; this is particularly relevant for cotinine. We will conduct several preliminary analyses prior to addressing the Study Aims: (1) Examination for out of range values; (2) Comparison of baseline characteristics of caregivers and children across groups. If baseline differences are found, further analyses will include these variables as covariates in assessing caregiver and child outcomes as appropriate; and (3) Attrition analyses to assess if: Participants who were lost to follow-up are different from those retained. Although we do not expect differential attrition by group, it will be evaluated and if it occurs, we will weight the follow-up data to reflect the proportion assigned to each group. If key variables significantly predict attrition, we will examine the analysis with and without the drop-outs. Thus, we will compare our primary outcomes using a multiple imputation approach for missing data to allow maximum utilization of our data. When including those that were lost to follow-up, the outcome data may be weighted using a response propensity analysis^{94,95} which uses the baseline distributions on these variables so that follow-up data has the same distributions on these variables as the baseline data. For all analyses we shall include in the model an indicator variable to account for which clinical counselor/intake coordinator/research coordinator was involved in the delivery of the SBIRT or HHC.

General approach for addressing study aims. This is a two-group RCT, wherein caregivers are randomly assigned to the SBIRT Group vs. HHC group. The appropriate statistical models for analyses of data for inclusion of time dependent outcomes are General Linear Mixed Models (GLMM) for data either with a Gaussian/normal distribution or with a binomial or Poisson distribution, using the appropriate link function, invoking Generalized Estimating Equations (GEE) to account for the longitudinal aspect of the data.⁹⁶

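### Prolonged abstinence yields too few events for the counsellor indicators that the plan puts in the primary model; as fixed effects they can make the treatment effect inestimable

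*Combined protocol and SAP*

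**What the plan says.** All references are to the combined protocol and SAP.

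- **Rates** (Sample Size and Power Estimates): "For prolonged abstinence, we are basing our estimation on the 2.1% rate for the HHC and 7% rate for SBIRT".
- **Numbers** (same section): enrolment of 750 is "adjusted for potential attrition of approximately 20% at 6 months", "leaving a total of 600; 300 per group". Table 2 uses 375 per group when multiple imputation is assumed.
- **Detectable difference** (Power): "For 6-month abstinence, we can detect an increase of 4.5% with 300 subjects per group and 4.2% with the multiple imputation assumption".
- **Counsellor term** (Preliminary Analyses): "For all analyses we shall include in the model an indicator variable" for the person who delivered the session. Primary Aim 1, Hypothesis 1 repeats this: the primary approach is multiple imputation with counsellors in the model.
- **Who delivers what** (counsellor activities, training and monitoring): three or more staff deliver SBIRT and three or more deliver HHC. The screening and enrolment section describes coverage by pairs, one member from each condition.
- **Follow-on model** (Primary Aim 1, Hypothesis 1): an analysis of covariance then adds variables that differ at baseline and the contemplation ladder score. For motivation and caregiver gender, the stratification factors, "we will initially enter this into the model as an interaction".
- **Strata** (Randomization): eight, from gender and four levels of readiness.

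The plan does not say whether counsellor is a fixed or random effect, whether motivation enters the interaction as stage or as ladder score, or whether treatment is part of it. It gives no rule for dropping terms and no fallback for separation.

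**The concern.** Prolonged abstinence is one of two primary caregiver outcomes and by far the rarer. The Power section calls the sample more than sufficient for regression, but argues from correlations and never counts abstinence events.

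A logistic model has no finite maximum-likelihood coefficient for a group without events. If that group is a stratum common to both arms, the damage is confined to that stratum's coefficient. If it is a counsellor who worked in one arm only, it reaches the treatment contrast, because that contrast is built from the counsellor-specific log-odds. The counsellor term is therefore the one to worry about, and the plan puts it in the primary model.

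With no fallback written down, the response to a failed fit would be chosen after seeing the data. The word initially in the interaction sentence leaves the same opening in the covariate model.

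**Working it through.** **1. The plan's own figure.** Alpha and sidedness are not given for this calculation; I assume 0.05, two-sided. An increase of 4.5 points means 2.1% against 6.6%, with odds ratio (0.066/0.934)/(0.021/0.979) = 3.29, as in Table 2. By the arcsine method, h = 2·asin√0.066 − 2·asin√0.021 = 0.229, and power = Φ(0.229·√(300/2) − 1.96) = 80%. The stated figure reproduces. A pooled two-proportion test gives 77.2%. None of these calculations contains a counsellor term.

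**2. Expected events.**

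| Analysis set | HHC (2.1%) | SBIRT (7%) | Total |
|---|---|---|---|
| Completers, 300 per arm | 6.3 | 21.0 | 27.3 |
| Imputed, 375 per arm | 7.9 | 26.3 | 34.1 |

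The extra seven or so events in the second row are imputed, not observed.

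**3. Aliasing.** Take three counsellors per arm. An intercept, a treatment indicator and five counsellor indicators make 7 columns, but there are only 6 distinct counsellor groups, so the rank is 6. Treatment is estimable only after a constraint is imposed, for example counsellor effects summing to zero within each arm. The plan names none.

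**4. Chance that some HHC counsellor has no events.** Assume equal caseloads and k counsellors per arm. P(one has none) = q = 0.979^(n/k), and P(at least one has none) = 1 − (1 − q)^k.

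| n per arm | k | Clients each | q | P(at least one) | Simulated |
|---|---|---|---|---|---|
| 300 | 3 | 100 | 0.120 | 32% | 32% |
| 375 | 3 | 125 | 0.070 | 20% | 20% |
| 300 | 6 | 50 | 0.346 | 92% | 93% |
| 375 | 6 | 62.5 | 0.265 | 84% | 85% |

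**5. Effect on the treatment estimate.** Logistic fits were simulated at 2.1% and 7% with the sum-to-zero constraint and no true counsellor or stratum effect.

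- Three fixed counsellors per arm: treatment was not estimable in 30–35% of runs at 300 per arm and 19–26% at 375. Maximum-likelihood power at 300 per arm was about 47–56%, counting failed fits as non-significant. Firth fitting gave about 78–80%.
- Six fixed counsellors per arm: the treatment estimate was lost in about 83–90% of runs.
- Treatment and ladder score only, 300 per arm: separation in 0–0.3% of runs, treatment SE about 0.47, power about 81–85%.
- Main effects of gender and stage plus three fixed counsellors per arm: separation in 34–41% at 300 and 21–23% at 375, nearly all from the counsellor terms. Dropping the interaction alone does not cure the problem.

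**6. The interaction.** The fullest reading has treatment 1 + counsellors 4 + strata 7 + ladder 1 = 13 degrees of freedom, so 27.3/13 = 2.1 events each (34.1/13 = 2.6 with imputation). Ladder by gender needs only 8, or 27.3/8 = 3.4. The documents say only that fewer men are expected. With equally common stages at 300 per arm, some whole stratum has no events in about 94% of trials if 10% of caregivers are men, 70% if 20%, and 23% if 50%. With gender by stage and no counsellor terms, separation occurred in 70–97% of runs, yet treatment was lost in at most 0.3%, its SE stayed about 0.47 and power was 81–87%. With treatment inside the interaction, separation was 99.8–100% and power for the treatment term at most 8%.

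**The case against.** The strongest reply is that the plan never commits to fixed counsellor effects. Its general approach names mixed models, and a random counsellor effect nested in arm would remove the aliasing. That stands as a possible reading. But the text asks for an indicator variable, the usual wording for a fixed effect, and does not mention a random one.

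A second reply is that the primary analysis is imputed, so about 34 events rather than 27 are expected. That is right, and the 375-per-arm figures belong beside the others. The risk falls but does not vanish: 20% with three counsellors per arm, 85% with six.

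A third concerns the interaction. A reader might infer that the plan states one model of 13 or more terms, and that the interaction will make the primary result fail. The documents do not support this. The interaction appears in a covariate model that follows the primary one. The preceding sentence speaks of the ladder score, so it may be ladder by gender, which adds little separation. Treatment is not named as part of it. Even in the gender-by-stage form, empty strata leave the treatment estimate intact. This objection stands in full.

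**Conclusion.** The concern holds for the counsellor term. With 27 to 34 expected events and counsellors nested in arm, fixed indicators in the primary prolonged-abstinence model are aliased with treatment. With three per arm they leave the treatment log-odds ratio inestimable in roughly one trial in five to one in three, and with six per arm in most trials. At 300 per arm with three each, maximum-likelihood power falls to about half.

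For the interaction only a weaker statement holds: separation is probable if it uses the four-level stage and few caregivers are male, and it damages stratum coefficients. It would threaten the treatment estimate only if treatment were included, which the plan does not say.

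These sizes rest on the plan's rates, equal counsellor caseloads, fixed coding, two-sided 0.05 and, for the strata, an assumed share of men. Uneven caseloads would change the figures. Point prevalence, planned at 6.3% and 12%, has more events and is not covered by these numbers.

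**What to change.** Write the prolonged-abstinence model into the SAP before unblinding:

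1. **Primary model:** treatment plus main effects of gender and readiness stage, no interaction, fitted by Firth penalised logistic regression within each imputed dataset and pooled.
2. **Counsellor:** exempt this model from the rule that every analysis carries a counsellor indicator. Handle counsellor as a random effect nested in arm, or in a sensitivity analysis, and say which. Keeping fixed indicators under Firth would give finite estimates but leave the aliasing unresolved.
3. **Supporting estimate:** a Mantel-Haenszel risk difference stratified by the randomisation factors, which needs no stratum coefficients.
4. **Interaction:** move gender by motivation to a secondary analysis of point prevalence. State whether motivation is stage or ladder score, and whether treatment is included.

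The cost is SAP wording. The downside is fewer covariates for this outcome: the ladder score and any variables that differ at baseline leave its primary model, and counsellor differences are not adjusted as fixed effects.
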